2.3 Aims/Objectives/Research questions

The overarching NIHR grant includes three related studies that together make an important contribution to the overarching evaluation of the impact of MUP in Scotland. The three research

aims and their associated studies are summarised in the Table below. The remainder of this protocol will only focus on the Emergency Department (ED) study, with a separate protocol available for the survey of alcohol-related behaviours (which involves data collection within sexual health clinics).

Research aims (RAs)	Study components
RA1: To determine the impact on alcohol-related harms	Emergency Department study;
and drinking patterns for the overall population and by	Survey of alcohol-related
subgroups of interest (age, sex and deprivation)	behaviours (C1)
RA2: To determine the impact on non-alcohol substance	Survey of alcohol-related
use for the overall population and by subgroups of interest	behaviours(C2); Qualitative focus
(age, sex and deprivation).	group study (C3)
RA3: To describe changes in experiences and norms	Qualitative focus group study (C3)
towards MUP and alcohol use following the introduction of	
MUP by subgroups of interest (age, sex and deprivation).	

The more specific research objectives (ROs) of the ED study are as follows:

- 1. To determine the impact of MUP on alcohol-related ED attendances amongst the general population
- 2. To determine whether the effect of MUP differs across the following population subgroups
 - a. Age group
 - b. Gender
 - c. Area-based deprivation
- 3. To determine whether the effect of MUP varies dependent on the type of alcohol-related harm:
 - a. Acute alcohol-related harms vs chronic alcohol-related harms
 - b. Broad diagnostic groups (on the basis of ICD categories)
- 4. To investigate whether alcohol consumption (on the basis of the FAST score: sensible, hazardous, harmful, possible dependence) has changed amongst people attending EDs over time
- 5. To investigate whether the intervention effect size varies over time

3 Study Design/Methods

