Since the design of the study is by necessity non-randomised, there remains potential for confounding. Furthermore, given the need to include high-risk drinkers within the study, previous experience has demonstrated that it is not possible to conduct longitudinal research with satisfactory rates of follow-up. For this reason, repeated cross-sectional samples have been chosen. However, the validity of analysis of repeated cross-sectional samples require high response rates and for participants interviewed to be representative of the population from which they are drawn (i.e. attenders to the ED in this study). It is therefore crucial that considerable effort is made to ensure that all eligible patients attending ED during data collection periods is invited to participate. The absolute number of participants within the study is far less important.

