3.3 Participant Selection

The target population for the study is all patients over 16 years age who attend EDs to receive acute treatment for a health condition.

The exclusion criteria for the sample are used to decide whether to approach patients and having approached whether the patient is eligible:

Deemed clinically inappropriate to be approached.

- 'patient too unwell',
- · too distressed,
- grossly intoxicated (alcohol),
- grossly intoxicated (drugs)
- Cognitive impairment
- · Police in attendance,
- Clear language barrier, and no interpreter available
- · Patient already participating,
- routine follow up that has been instigated by ED staff,
- Patient left dept
- Patient admitted,
- staff safety issue,
- End of shift,
- dead on arrival,
- other.

For those who are approached, the inclusion criteria are:

- >=age16
- able to speak English and no interpreter available.
- Is a new ED presentation,
- The patient is conscious
- The patient is physically well enough
- The patient is mentally well enough
- The patient is sober enough (alcohol)
- The patient is sober enough (drugs)
- The patient is still in the department
- The patient is safe for staff to approach

During data collection periods, an ED attendance database will be maintained for all attendances to allow monitoring of patient recruitment. This will help prevent patients being approached on multiple occasions. This attendance database will be destroyed at the end of each recruitment shift. In addition, data on sex, five year age group and diagnoses for all attendees in all the three week waves, with the attendees within the study timeslots flagged, will be requested from hospital records. This is to enable the assessment of the representativeness of our sample and of our estimates of the proportion of alcohol-related attendances.

We intend to obtain a total sample size of at least 2820 participants across all four sites over each three week period of data collection. This equates to 235 participants per week per site of data collection. No target sample size is required for the pilot phases of the study as these phases are intended to help identify potential practical issues involved in conducting the study.

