3.7 Data Collection

Each wave will collect data over three weeks, ideally with one wave of data collection prior to the implementation of MUP and two post-implementation waves (after six months and 12 months). To maximise collection of both alcohol-related attendances and hazardous drinkers, data collection will occur from 2000 to 0400 on Thursday to Sunday (i.e. 32 hours per week during this time period) and 0900-1700 on Monday to Wednesday (i.e. 24 hours per week during this time period). If deemed necessary by local sites, different 8 hour timeslots will be considered, to meet local attendance patterns. As noted above, periods of the year when alcohol consumption is atypical will be avoided.

Patients will be approached by research staff to seek permission to complete a short face-to-face interview. The reasons for exclusion will be recorded electronically on the iPad along with 5 year age group and sex. Excluded patients will not be assigned a study ID and so will be completely anonymous.

All suitable patients will be approached, their eligibility confirmed, and, if eligible, informed consent will be sought and a face-to-face interview administered, based on a previously used patient questionnaire [36]. Research nurses will be responsible for obtaining written informed consent, completing the data linkage form if consent has been obtained -and then proceeding to conduct the face-to-face survey. These will all be electronic documents contained on an iPAD.

The face-to-face survey will collect information on socio-demographic details, problematic alcohol use (FAST Alcohol Screening Test), alcohol consumption in the last 24 hours, self-assessment of whether alcohol contributed to the attendance and self-report of whether the patient has been a victim of violence. Research nurses will input the information into the standardised electronic form which will include a number of options to assist with timely completion. Paper versions of the survey, and consent and linkage forms are enclosed (ED Survey v2.5). The Interview Schedule for Pilot Phase v2.5 and Qualitative Interview for Pilot Phase will be on paper only. Back up paper copies of all electronic documents will be available in case of iPad failure. An ED attendance database will be maintained for all attendances during data collection periods to allow monitoring of patient recruitment.

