Research staff will retrieve additional data on participants from patient records, either during data collection sessions (if time allows), or at a later time. The following information will be sought from the clinical records:

- demographic characteristics (date of birth, sex, postcode),
- attendance details (time, triage category),
- discharge status
- diagnoses at discharge (coded by ICD10 categories) and all relevant data relating to reason for admission and diagnosis (whether ICD10 or another coding system or free text).

We will calculate the consent rate among those eligible. However we need to assess the representativeness of the interviewees and attendees in the study timeslots, and the certainty of our estimates of the proportion of attendances that are alcohol-related. To make this possible, we propose to request from hospital records anonymised information on all attendees over the three week data collection periods for each wave. We wish to ask for 5 year age groups, sex, reason for attendance, and other relevant data for diagnosis (whether ICD10 or another coding system or free text). We will request that attendees within the timeslots for the study are flagged, so that we can calculate a true recruitment rate for those interviewed and for whom we have reasons for exclusion.

Data collection will be conducted by Clinical Research Facilities (CRFs), on behalf of the study team. Each CRF will be responsible for ensuring line management of their staff, as per their usual operating procedures. The research nurses responsible for data collection will have received training, with training available for additional research nurses (to allow for rota gaps to be filled, in the event of illness etc.). It is recommended that any data collection session should include at least one more experienced research nurse, so that more junior research nurses feel adequately supported. Research nurses will be able to contact a member of the study team throughout data collection periods in the event of an emergency.

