3.8 Data Analysis

Primary outcome

The primary outcome will be changes in absolute numbers of alcohol-related attendances as defined by any one of:

- patient self-reports attendance is alcohol-related
- patient reports alcohol consumption in past 24 hours of ≥8units in men or ≥6 units in women
- patient not approached because too intoxicated with alcohol

Secondary outcomes

Secondary outcomes will be changes in:

- absolute number of alcohol-related attendances by age/sex/deprivation
- problematic alcohol use (as defined by the Fast Alcohol Screening Test (FAST))
- mean FAST score
- prevalence of binge drinking in the past week
- reason for attendance (coded by ICD10)

After the first post-intervention wave, we will test for differences in the outcomes between the intervention and comparison groups using a fixed-effects regression model, with individuals nested within EDs, before and after adjustment for relevant covariates including baseline levels of alcohol-related attendance, demography, triage category etc. We will also attempt to determine the nature of the effect more precisely in terms of whether a dose-response effect according to the time since MUP was implemented (through a test of the significance of an interaction between time and intervention). We will test for interactions of the intervention with defined important covariates (including age, gender, deprivation quintile, disease diagnostic categories) to investigate the possibility of differential intervention effects and will subsequently stratify the analyses if indicated.

4. Research Governance and Regulatory Issues

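### The all-attendee extract carries no deprivation measure, so recruitment by deprivation cannot be calculated and the planned counts by deprivation cannot be scaled to all attendees.

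*Protocol*

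**What the plan says.** Deprivation is one of the protocol's named axes. Objective 2c in section 2.3 is "Area-based deprivation". The secondary outcomes in section 3.8 include "absolute number of alcohol-related attendances by age/sex/deprivation", and the same section plans an interaction test of the intervention with deprivation quintile.

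The protocol describes what is held on each group of patients:

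- **Participants.** Section 3.7: "Research staff will retrieve additional data on participants from patient records". The list begins with "demographic characteristics (date of birth, sex, postcode", so deprivation can be derived for them.
- **Excluded patients.** Section 3.7: "The reasons for exclusion will be recorded electronically on the iPad along with 5 year age group and sex". They receive no study ID, so nothing can be attached later.
- **All attendees.** The extract is described twice. Section 3.3 lists "data on sex, five year age group and diagnoses for all attendees in all the three week waves", with those in the study timeslots flagged. Section 3.7 says "We wish to ask for 5 year age groups, sex, reason for attendance, and other relevant data for diagnosis". Both places give its purpose as assessing representativeness, and section 3.7 adds calculating a true recruitment rate.
- **ED attendance database.** Section 3.3 has it destroyed after every recruitment shift.

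Section 3.1 states the condition on which the design rests: repeated cross-sections "require high response rates and for participants interviewed to be representative of the population from which they are drawn".

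**The concern.** The extract is the study's only lasting source on people who were not interviewed. It covers two of the three axes in the secondary outcome, age and sex, but not deprivation. The outcome is an absolute number, and section 3.3 assumes recruitment of at least 50% of eligible attendees, so up to about half may not be interviewed. A count taken from interviews rises and falls with the share of patients interviewed.

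If recruitment among deprived patients changes between waves, and does so differently in Scotland and England, the deprivation-specific count changes too. The study would have no denominator with which to tell this apart from an effect of pricing. Differential impact by socioeconomic group is a stated reason for the research (section 2.1), so the gap bears on a question that matters to the sponsor.

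A statistical analysis plan cannot repair this. It cannot weight by a variable that was never obtained for non-participants.

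**Working it through.** **1. Can a recruitment rate by deprivation be formed?** It needs interviewees by quintile over attendees by quintile.

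| Source | Age, sex | Deprivation |
|---|---|---|
| Participants (3.7) | yes | yes, from postcode |
| Excluded patients (3.7) | yes | no |
| All-attendee extract (3.3, 3.7) | yes | no |
| ED attendance database (3.3) | destroyed each shift | destroyed each shift |

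The numerator exists and the denominator does not. The closing phrase of the section 3.7 field list is confined to diagnosis and cannot be read as covering an area measure. Linkage to administrative records (section 3.4) requires consent and so does not reach non-participants.

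**2. The plan's own figures.** 235 per week per site × 4 sites × 3 weeks = 2820 per wave, and 940 × 3 × 2 = 5640. For 30% versus 25% at two-sided 5%, power = Φ[(0.05 − 1.96·SE₀)/SE₁], with SE₀ = √(2 × 0.275 × 0.725/n) and SE₁ = √((0.30 × 0.70 + 0.25 × 0.75)/n).

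- n = 2820 per group: 98.8%
- n = 1410 per group: 84.5%

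The stated power above 80% reproduces. The point here does not depend on it.

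**3. Size on the count scale.** Inputs from section 3.3: 50% recruitment, 25% of attendances in the most deprived quintile, 30% alcohol-related. Assumptions: equal recruitment by site, the 30% applied within the quintile, and all alcohol-related cases found at interview.

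- Scottish interviewees per wave: 235 × 2 × 3 = 1410
- Most deprived quintile: 1410 × 0.25 = 352.5
- Alcohol-related: 352.5 × 0.30 = 105.75, about 106

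Let that quintile's recruitment change from r₀ to r₁ with no change in harm. The observed count becomes 105.75 × r₁/r₀.

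| r₀ to r₁ (assumed) | Count | Change |
|---|---|---|
| 50% to 47.5% | 100.5 | −5% |
| 50% to 45% | 95.2 | −10% |
| 50% to 42.5% | 89.9 | −15% |

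The same 5-point fall gives −12.5% from a 40% start (35/40) and −8.3% from a 60% start (55/60).

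**4. What the same drift does elsewhere** (50% to 45%).

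- Interviewees in the quintile: 352.5 × 0.9 = 317.25. Proportion alcohol-related: 95.175/317.25 = 30%, unchanged.
- Quintile's share of interviewees: 0.25 × 0.45/(0.75 × 0.50 + 0.25 × 0.45) = 0.1125/0.4875 = 23.1%, down from 25%.
- Interviewees in the quintile whose attendance was not alcohol-related: 352.5 × 0.70 = 246.75, falling to 222.1.
- Sampling noise: the Poisson SD of a difference between two counts of 105.75 is √(2 × 105.75) = 14.5, so a shift of 10.6 is about 0.7 SD.
- Scotland-to-England ratio of relative change: 0.90/0.90 = 1 if both countries drift alike, 0.90 if only Scotland does.

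**5. The third outcome component.** Under section 3.8, patients not approached because of alcohol intoxication count as alcohol-related. Section 3.7 records only reason, age group and sex for them, so they cannot be placed in any deprivation group.

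**The case against.** The strongest reply is that the drift is assumed and harms only one scale. Nothing in the protocol suggests a 5-point fall confined to one quintile. If recruitment falls equally for alcohol-related and other patients in that quintile, the proportion among interviewees is untouched. A regression of alcohol-related status among interviewees, which section 3.8 could be read to allow, would be unbiased by it. The English sites would absorb drift common to both countries, and the shift is smaller than the sampling noise in a single comparison of two counts. All of this stands. It limits the size of the point but does not remove it, because section 3.8 specifies absolute numbers and without denominators nobody can check whether drift was absent or common.

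A reader might infer three stronger things that the documents do not support.

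- **That the drift equals a large part of the effect the study is sized for.** The 30% to 25% target in section 3.3 is a whole-sample proportion. For the most deprived quintile that section sizes only a FAST effect of 0.23, so no fall in a quintile's count was sized for.
- **That the study would be blind to the drift.** Interviewees' postcodes are held, so their deprivation mix is visible by site and wave. A move from 25% to 23.1%, with alcohol-related and other interviewees falling together, is a signal. It is inconclusive, because case mix may also change.
- **That the planned comparison by age, sex and diagnosis would show nothing.** This cannot be shown from the protocol. Such a check may pick up drift that correlates with those variables, though it could not attribute it to deprivation.

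Dependence of interview-based counts on recruitment also affects the primary outcome and the age and sex splits. The difference is that the extract would permit scaling by age and sex, although the protocol does not say this will be done.

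**Conclusion.** The point holds as a gap in the data to be collected. Deprivation is available for interviewees only. Recruitment by deprivation cannot be calculated, and the planned counts by deprivation can be neither scaled to all attendees nor separated from recruitment that changes differently by deprivation across waves and countries.

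The 10% figure is illustrative. It rests on the protocol's planning values, an assumed fall from 50% to 45% in one quintile, equal recruitment by site, and the count scale. It is not evidence that such drift will occur, and it does not carry over to the proportion among interviewees.

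Separately, and whatever the recruitment, the deprivation-specific counts as planned omit the patients too intoxicated to approach. The overall primary outcome is not undermined by this gap. It is a worthwhile and inexpensive improvement for objective 2c and one secondary outcome.

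**What to change.** 1. Add area-deprivation quintile to the extract fields in both section 3.3 and section 3.7, derived from postcode by the hospital before release so that no postcode leaves the site.
2. Report recruitment by quintile, site and wave.
3. Weight or scale the interview-based deprivation-specific counts to all attendees in the flagged timeslots, by quintile, age and sex.
4. Record quintile, not postcode, on the exclusion record where feasible, at least for patients not approached because of alcohol intoxication. The extract column alone cannot supply this, since excluded patients have no study ID. If it is not feasible, state that the deprivation-specific counts omit that outcome component.

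The cost is a line in the data request and the ethics amendment, plus more disclosure control for small cells. The protocol does not show whether every site can derive quintiles, so this should be confirmed with the sites first. Weighting by quintile will not remove non-response related to drinking within a quintile, and the report should say so.

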3.8 Data Analysis

Primary outcome

The primary outcome will be changes in absolute numbers of alcohol-related attendances as defined by any one of:

- patient self-reports attendance is alcohol-related
- patient reports alcohol consumption in past 24 hours of ≥8units in men or ≥6 units in women
- patient not approached because too intoxicated with alcohol

Secondary outcomes

Secondary outcomes will be changes in:

- absolute number of alcohol-related attendances by age/sex/deprivation
- problematic alcohol use (as defined by the Fast Alcohol Screening Test (FAST))
- mean FAST score
- prevalence of binge drinking in the past week
- reason for attendance (coded by ICD10)

After the first post-intervention wave, we will test for differences in the outcomes between the intervention and comparison groups using a fixed-effects regression model, with individuals nested within EDs, before and after adjustment for relevant covariates including baseline levels of alcohol-related attendance, demography, triage category etc. We will also attempt to determine the nature of the effect more precisely in terms of whether a dose-response effect according to the time since MUP was implemented (through a test of the significance of an interaction between time and intervention). We will test for interactions of the intervention with defined important covariates (including age, gender, deprivation quintile, disease diagnostic categories) to investigate the possibility of differential intervention effects and will subsequently stratify the analyses if indicated.

4. Research Governance and Regulatory Issues

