Based on the experience of the 24 hour audit of Emergency Departments in England, we have assumed that we will be able to recruit at least 50% of eligible ED attendees. We anticipate that the four sites will result in 940 recruits per week. Recruiting over three weeks pre- and post-intervention – giving a total sample size of 5640 – would mean that we would be highly powered (>80%) to detect a decrease in the proportion of alcohol-related attendances from 30% to 25% with 95% significance. We have used a base rate of 30% informed by the 24 hour audit of EDs in England and assumed a 5% decrease would be of public health importance and may be expected based on current evidence. For subgroup analyses, we would have good power (>80%) to detect an effect size of 0.23 on the FAST score among those from the most deprived quintile (estimated to be 25% of attendances) and an effect size of 0.27 among those aged 18-24 (estimated to be 15% of attendances. Two separate follow-up times are required to determine if intervention effects vary over time.

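### The primary outcome is a raw count that depends partly on recruitment, while the sample size is set on a proportion; outcome, denominator and power need to be put on one recruitment-adjusted scale.

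*Protocol*

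**What the plan says.** - Protocol 3.8, Primary outcome: "The primary outcome will be changes in absolute numbers of alcohol-related attendances as defined by any one of" three criteria. These are the patient's own report that the attendance is alcohol-related, a threshold of units in the past 24 hours (8 for men, 6 for women), or "patient not approached because too intoxicated with alcohol". No denominator, offset or scaling is given. The first secondary outcome, by age, sex and deprivation, is also an absolute number.
- Protocol 3.3, sample size: the power claim is "to detect a decrease in the proportion of alcohol-related attendances from 30% to 25% with 95% significance". The starting value is explained as "We have used a base rate of 30% informed by the 24 hour audit of EDs in England".
- Protocol 3.3, recruitment: "we have assumed that we will be able to recruit at least 50% of eligible ED attendees". The target is 2820 participants per wave over four sites.
- Protocol 3.3 and 3.7: anonymised records on all attendees are to be requested, with those in the study timeslots flagged. One stated purpose is to judge the representativeness "of our estimates of the proportion of alcohol-related attendances". Another is to obtain a true recruitment rate. Adjusting the primary outcome is not among the stated uses.

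**The concern.** The primary outcome and the sample size are on different scales, and the scale chosen for the outcome is open to an artefact. The first two criteria are observed only in people who consent and are interviewed. The third comes from the exclusion record and does not depend on consent. So most of what is counted is a sample taken at some recruitment fraction, and the rest is a full count.

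If that fraction changes between waves in one country and not in the other, the raw count changes with it, whatever the policy has done. A recruitment change could then be read as an effect of minimum unit pricing, or could conceal one. With two EDs per country there is little averaging to protect against this. The power statement, meanwhile, does not describe the outcome that section 3.8 says will be tested.

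**Working it through.** **Inputs.** From 3.3: 235 participants per site per week, three weeks per wave, 30% falling to 25%, recruitment 50% (stated as a floor), power above 80%. The significance level is given as "with 95% significance"; I take this as two-sided 0.05. From 3.1: two Scottish and two English sites.

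**1. The plan's own figures.** 235 × 4 = 940 per week; × 3 = 2820 per wave; × 2 = 5640. Two sites in one wave give 235 × 2 × 3 = 1410.

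Power for two proportions (pooled variance under the null) is Φ{[0.05√n − 1.96√(2 × 0.275 × 0.725)] / √(0.30 × 0.70 + 0.25 × 0.75)}.
- n = 1410 per group: (1.8775 − 1.2377) / 0.6305 = 1.015, power 84.5%.
- n = 2820 per group (all four sites, before v after): power 98.8%.

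The stated figure reproduces, as a two-group comparison of proportions.

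**2. How the interview-based count moves with recruitment.** For the two Scottish sites, 1410 / 0.50 = 2820 eligible attendees. Count = 2820 × recruitment fraction × alcohol-related rate.

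| True rate | Recruitment | Count | Change from 423 |
|---|---|---|---|
| 30% | 50% | 423 | – |
| 25% | 50% | 352.5 | −16.7% (planned effect) |
| 30% | 45% | 380.7 | −10% |
| 30% | 41.7% | 352.5 | −16.7% (no true effect) |
| 25% | 60% | 423 | 0 (true effect hidden) |

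The two critical fractions are 0.50 × 25/30 = 0.417 and 0.50 × 30/25 = 0.60.

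**3. False positives, as an illustration.** Assume Poisson counts, no true effect, England constant at 423 in both waves, and a Scotland–England contrast of log count ratios. With Scottish recruitment at 45%, SE = √(3/423 + 1/380.7) = 0.0986 and ln(0.9) = −0.105, so the test rejects about 19% of the time instead of 5%. At 47.5% it rejects about 8%; at 41.7%, about 45%.

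**4. Power on the count scale.** Assume a Poisson comparison of Scottish interview-based counts before and after. SE = √(1/423 + 1/352.5) = 0.0721; |ln(25/30)| = 0.182; power = Φ(0.182/0.0721 − 1.96) = about 72%. Pooling all four sites (846 v 705) gives about 95%, but that supposes the same fall in the English control sites.

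**5. Whether a plain proportion would cure it.** Suppose 2820 attenders, 846 alcohol-related (30%), of whom 146 are too intoxicated to approach. The 146 is assumed for illustration. That leaves 700 alcohol-related patients among the other 2674.
- Pooled without weights, 50% recruitment: (350 + 146) / (1337 + 146) = 33.4%.
- Pooled without weights, 41.7% recruitment: (292 + 146) / (1115 + 146) = 34.7%.
- Interviewees weighted by the inverse of recruitment: (350/0.50 + 146) / 2820 = 30.0%, and the same at 41.7%.

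In this example the whole raw count goes from 496 to about 438, a fall of about 12%. That is smaller than 16.7% because the too-intoxicated patients do not move with recruitment.

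**The case against.** Several stronger readings are tempting, and the protocol does not support them.

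- **That the plan uses a proportion everywhere except in the primary outcome.** It does not. The first secondary outcome is also a number, the first objective in 2.3 speaks of attendances without naming a proportion, and 3.1 describes an audit of all alcohol-related attendances. The burden on EDs is a legitimate target, and a correctly scaled count would be defensible.
- **That the regression in 3.8 cannot estimate a change in counts.** The text gives no link or distribution, and the same sentence also covers mean FAST score. Individuals nested within EDs suits a probability better, but the exact form may lie in an analysis plan that is not at hand.
- **That recruitment will differ between EDs and waves.** Nothing in the protocol shows this. The 50% is an assumed minimum, 3.7 asks for consistent processes across sites and over time, and a shared change cancels in a relative contrast with England.
- **That 3.1 contradicts the outcome by saying "The absolute number of participants within the study is far less important".** That sentence weighs sample size against response rate. It does not concern the number of alcohol-related attendances.
- **That the count scale alone takes power from above 80% to 45%.** The 45% is for an assumed four-cell Scotland–England, before–after contrast on counts. The same contrast on proportions gives about 55%, so most of the drop comes from the contrast and about 10 points from the scale.

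The requested all-attendee records also mean that the inputs for scaling are already planned. That makes the repair easy, but 3.8 does not apply them to the primary outcome. The mismatch of scales and the missing denominator therefore stand.

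**Conclusion.** The point holds. As written, the primary outcome lets a differential change in recruitment create or hide the whole target effect in the interview-based part of the count, and the power claim belongs to a different scale. An unseen analysis plan does not settle this, because the protocol itself names the outcome and the powered quantity, and they differ.

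The size of any bias is conditional. It needs a recruitment change in one country and not the other; the shifts to 41.7% and 60% are hypothetical and start from the assumed 50%; and it applies in full only to the interview-based criteria. The 72% and the false-positive rates rest on a Poisson model that the protocol does not state, and ignore clustering by ED. A reader might infer that replacing the count with any proportion is enough. It is not, because the too-intoxicated patients are logged in full while the others are sampled, and pooling the two without weights leaves a proportion that still depends on recruitment.

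**What to change.** In 3.8, replace the raw count with the recruitment-adjusted proportion of study-timeslot attendances that are alcohol-related, by ED and wave.

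- **Numerator:** patients logged as too intoxicated with alcohol, counted in full, plus alcohol-related interviewees weighted by the inverse of the recruitment fraction in that ED and wave, within age group and sex where numbers allow. To match the denominator, that fraction should be interviewees divided by timeslot attendances not logged as too intoxicated.
- **Denominator:** all timeslot attendances from the flagged hospital extract already requested in 3.7.
- **Companion secondary outcome:** the scaled-up number, which is that proportion times total timeslot attendances. It is needed because the proportion's denominator also shrinks if the policy removes attendances.
- **Subgroups:** make the same change to the numbers by age and sex. The all-attendee extract does not list postcode or deprivation, so for deprivation report the proportion among interviewees rather than numbers.
- **Sample size:** restate the power in 3.3 for the chosen scale and for the contrast that will be tested.

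The cost is protocol wording and some extra analysis; the extract and the exclusion log are already planned. The added assumption is that, within weighting cells, interviewees represent the attenders who were not interviewed.
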